7.2.2. Safety and Data Monitoring Committees

No safety and data monitoring committee has been established for this study.

7.2.3. Interim Analyses

No interim analyses will be performed in this study.

7.2.4. Expected Duration of Study

The duration of this study is expected to be approximately 38 days per subject (excluding the screening period). The actual overall study duration and study recruitment time may vary.

7.2.5. Screening

Within 21 days before the first administration of IMP and after written informed consent is obtained, screening procedures will be performed on each potential subject (see [Table 7-1](#)). Subjects who meet the inclusion criteria ([Section 7.3.1](#)) will be considered eligible to participate in the study. Subjects who meet one or more of the exclusion criteria ([Section 7.3.2](#)) will not be considered eligible to participate in the study.

At the discretion of the PI, vital signs and laboratory investigations of variables outside the reference ranges may be repeated up to 3 times. Should the variables return to within the reference range, or should the PI consider the variable to be at an acceptable level in relation to the reference range, the persons will be considered eligible to participate in the study.

7.2.6. Treatment Periods

Each treatment period will include a profile period of 12 hours on Day 1 and 24 hours on Day 7 and dosing twice daily on Days 1, 2, 3, 4, 5 and 6 and only in the morning on Day 7.

Subjects will be admitted to the study center on Day -1 and on the evening of Day 5.

Details on the requirements for storage of IMP at home, instructions on administration of IMP and completing of the diary card will be communicated to the subjects in an information leaflet.

Training of Self-administration

IMP will be self-administered. Subjects will be trained by the study staff on Day -1 of each treatment period to administer the IMP on one of the upper thighs. An area of about 20 cm² will be marked with a black skin marker pen.

One thigh should be used during the study. During one treatment period (out of 3) one thigh MUST be used. If this is not possible for safety reasons, then the patient will be discontinued.

If, after one period the subject suffers from skin irritation or non-intact skin (e.g., due to injury) the other thigh may be used for the following period.

The IMP will be administered twice (morning and evening) on Days 1 and 6 (12 hours \pm 10 min), twice on Days 2 to 5 (12 hours \pm 120 min) and in the morning only on Day 7. Each IMP administration will be recorded on a diary card.

Patients will be equipped with disposable gloves and instructed to wear them whenever applying the IMP. An area of approximately 20 cm x 20 cm (corresponding to approximately 2 hand sizes) will be treated. A gel drop of approximately the size of a hazelnut will be applied to the subject's gloved hand and quickly massaged into the skin until the whole amount of gel is absorbed. Each subject will have a new tube assigned per treatment period. The tubes will be weighed before and after dosing, whenever the subject is at the study center and the application site will be inspected by the Investigator at these time points as well. Refer to Schedule of Study Assessments in [Table 7-1](#).

Showering/bathing should be avoided for at least 1 hour before and after the application. External heat and/or occlusive dressings should not be applied to treated area. Wearing of clothing or covering the application area with clothes and/or blankets should be avoided for at least 10 minutes after applying the gel. Also refer to [Section 5.3](#) and [Section 7.2.10.1](#).

Before dosing on Day 1 and Day 7, an indwelling venous cannula will be inserted. The medical staff will decide when to remove or replace the venous cannula based on the time (since insertion of the cannula) or if clotting occurs. If the cannula is removed, the subsequent blood samples will be collected by venipuncture or the cannula will be replaced.

The cannula will be removed before discharge on Day 1 and Day 8 or as needed when not functioning properly any more as stated above.

Food and beverages restrictions are described in [Section 7.2.10.2](#).

Subjects will be allowed to leave the study center at least 24 hours after administration of the first dosing of IMP on Day 1 and at least 24 hours after the last dosing on Day 7.

7.2.7. Follow-up Evaluations

See [Table 7-1](#).

At the discretion of the PI, a follow-up physical examination will be performed on subjects withdrawn from the study due to an AE.

Follow-up laboratory investigations with variables outside the reference ranges will not necessarily be repeated to establish if and when those variables returned to within the reference ranges. The variables will be reviewed against the clinical background, other relevant investigations and their relevance to the administered IMP, before a decision will be made to repeat the investigations in question. At the discretion of the PI, the investigations of certain variables outside the reference ranges may be repeated until the variables return to within the reference range for the particular laboratory test, or until the PI considers the repeated variable to be at an acceptable level in relation to the reference range. If the Investigator has made every effort to contact the subject, but he/she remains unavailable to attend the clinic for repeat of applicable laboratory investigations, the Investigator may declare him/her lost to follow-up.

In cases where results of follow-up evaluations are reported after the database has been locked, the applicable clinical laboratory reports will be presented in the appendices to the clinical study report (CSR).

7.2.8. Sampling, Interim Handling and Storage

7.2.8.1. Safety Blood and Urine Samples

Refer to [Table 7-1](#).

Before starting the study, the Investigator (or designee) will supply the Sponsor with the reference ranges and units of measurement for the laboratory safety variables to be used during the study. If the reference ranges change during the course of the study, the Investigator (or designee) must provide the Sponsor with a list of the new reference ranges and the effective dates.

All safety blood and urine sampling will be performed by the study center, according to [REDACTED] standard operating procedures (SOPs).

The PI or designee will ensure that all biological fluids collected during the study will not be used for purposes other than as directed by the clinical study protocol. All collected biological fluids used for safety investigations will be destroyed within 3 months after the clinical execution of the study has been completed.

7.2.8.2. Pharmacokinetic Blood Samples

Pharmacokinetic blood samples will be collected as indicated in the Schedule of Assessments (Table 7-1). The actual blood sampling times will be recorded on source data/ClinBase™ and attached to the case report forms (CRFs).

Venous blood samples, 2 mL for the determination of diclofenac and 4 mL for the determination of capsaicin concentrations, will be collected into labeled potassium-ethylenediaminetetraacetic acid plastic (K₂-EDTA) tubes.

If not processed immediately, blood samples are to be placed on ice between sample collection and centrifuging. Within one hour of collection, centrifuging of blood samples will commence at approximately 2700 g within a range of 0°C to 8°C for 10 minutes. Thereafter, the supernatant of each sample will be divided into 2 aliquots (of at least 0.8 mL plasma each for capsaicin and 0.4 mL each for diclofenac) and transferred to labeled, plastic tubes and frozen immediately.

All sample tube labels will contain at least the following information: study number, analyte, time (protocol time and/or relative sampling time), subject number, blood sample number and treatment period. Plasma samples will be stored at -20°C in a temperature mapped freezer until transfer to ██████████ Bioanalytical Services Division (BASD). The labels of sample plasma tubes for capsaicin will be labeled similarly, but will not reflect the treatment period in order to keep the blind in the bioanalytical laboratory. Pooled samples for concentration range estimation will be prepared according to ██████████ SOPs. These specificity samples originate from some of the blood samples collected for drug assays and may be used by the analytical laboratory to determine suitable quantification ranges.

Unused duplicate plasma PK samples will be stored at BASD for 6 months after completion of the bioanalysis phase of the study. The Sponsor will be required to indicate whether additional storage is needed or whether the samples may be discarded.

7.2.9. Blood Volume

The total blood volume to be collected from each subject during the study is indicated in Table 7-2.

Table 7-2 Total Blood Volume to be Collected During the Study

Assay	Volume per sample (mL)	Total number of samples	Number of treatment periods	Total blood volume (mL)
Diclofenac (Day 1)	2	10	3	60
Capsaicin (Day 1)	4	10	1	40
Diclofenac (Days 5,6 and 7)	2	15 + 2(2)	3	114
Capsaicin (Days 5, 6 and 7)	4	15 + 2(2)	1	76
Hematology	4	2		8
Clinical chemistry*	5	2		10
Total blood volume (entire study)**				308

* Serum pregnancy tests (females only) and serology tests at screening will be performed on the sample collected for clinical chemistry

** Excluding repeat laboratory investigations

7.2.10. General and Dietary Restrictions

7.2.10.1. Posture

The IMP will be self-administered as described [Section 7.2.6](#). On Days 1 and 7, after dosing the subjects will remain in the supine position for 10 minutes before covering the dosing area with either clothing or blankets. Except for bladder voiding and ingestion of meals (where applicable), subjects will remain recumbent until 2 hours after administration of study medication, after which no restrictions concerning posture or movement will apply. Posture control procedures will be documented (see Source Data Agreement). For the application of the IMP at home and at the clinic on the other days the subjects will wait 10 minutes before covering the dosing area with either clothing or blankets, with no restrictions on posture or movement.

7.2.10.2. Diet

The ingestion of food and beverages containing citrus fruits and/or apple or pineapple will not be allowed for 72 hours before the administration of IMP and until the last PK blood sample is collected per treatment period.

The ingestion of food and beverages containing alcohol and/or methylxanthines e.g., caffeine (coffee, tea and cola) will not be allowed for 24 hours before the administration of IMP and until the last PK blood sample is collected per treatment period.

Food and beverage intake during the clinic stay will be standardized per treatment period. Meals taken during the clinic stay will be standardized in regard to composition and time of administration (see Source Document Agreement).

Water is allowed as desired. Food and beverage intake will be allowed *ad libitum*, unless restrictions apply, after the subjects have been discharged from the clinic.

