5.2. Clinical Pharmacokinetics

Capsaicin

In the current Investigator's Brochure (IB), studies examining higher strengths of capsaicin have found that, for a small proportion of patients, low, transient levels of capsaicin can be detected in the systemic circulation [5].

Voltarol

The information provided below is based on the approved product information as per the Summary of Product Characteristic (SPC) of Voltarol® 12 Hour Emulgel 2.32% Gel [1].

Absorption:

The quantity of diclofenac absorbed through the skin is proportional to the size of the treated area, and depends on both the total dose applied and the degree of skin hydration. After topical application to approximately 400 cm² of skin, the extent of systemic exposure as determined by plasma concentration of Voltarol® 12 Hour Emulgel 2.32% Gel (2 applications/day) was equivalent to diclofenac 1.16% gel (4 applications/day). The relative bioavailability of diclofenac (area under the plasma concentration-time curve [AUC] ratio) for Voltarol® 12 Hour Emulgel 2.32% Gel versus tablet was 4.5% on Day 7 (for equivalent diclofenac sodium dose). Absorption was not modified by a moisture and vapor permeable bandage.

Distribution:

Diclofenac concentrations have been measured from plasma, synovial tissue and synovial fluid after application of topical diclofenac to hand and knee joints. Maximum plasma concentrations were approximately 100 times lower than after oral administration of the same quantity of diclofenac, 99.7% of diclofenac is bound to serum proteins, mainly albumin (99.4%). Diclofenac penetrates inflamed areas, preferentially distributing to and persisting in deep inflamed tissues such as joints, where it is found in concentrations up to 20 times higher than in plasma.

Biotransformation:

Biotransformation of diclofenac involves partly glucuronidation of the intact molecule, but mainly single and multiple hydroxylation resulting in several phenolic metabolites, most of

which are converted to glucuronide conjugates. Two of the phenolic metabolites are biologically active, however, to a much smaller extent than diclofenac.

Elimination:

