7.3.2. Exclusion Criteria

1. Evidence of psychiatric disorder, antagonistic personality, poor motivation, emotional or intellectual problems likely to limit the validity of consent to participate in the study or limit the ability to comply with protocol requirements.
2. Current alcohol use > 21 units of alcohol per week for males and > 14 units of alcohol per week for females. One unit (10 g alcohol) is equal to beer (330 mL), wine (200 mL), or distilled spirits (25 mL) per day.
3. Regular exposure to substances of abuse (other than alcohol) within the past year.
4. Use of any medication, prescribed or over-the-counter (especially products containing diclofenac or use of other oral nonsteroidal anti-inflammatory drugs [NSAIDS]) or herbal remedies, within 2 weeks before the first administration of IMP except if this

will not affect the outcome of the study in the opinion of the PI (in collaboration with the Sponsor). In this study the concomitant use of hormonal contraceptives is allowed.

5. Participation in another study with an experimental drug, where the last administration of the previous IMP was within 8 weeks (or within 5 elimination half-lives for chemical entities or 2 elimination half-lives for anti-bodies or insulin), whichever is the longer before administration of IMP in this study, at the discretion of the PI.
6. Treatment within the previous 3 months before the first administration of IMP with any drug with a well-defined potential for adversely affecting a major organ or system.
7. A major illness during the 3 months before commencement of the screening period.
8. History of hypersensitivity or allergy (acute rhinitis, angioedema, urticaria or bronchial asthma) to the IMP or its excipients or any related medication (Aspirin or any other NSAID).
9. History of hypersensitivity or allergy to cayenne pepper or other capsaicinoids (paprika plants).
10. History of bronchospasm or bronchial asthma, arterial hypertension, myocardial infarction, thrombotic events, stroke, congestive heart failure, impaired renal function or liver disease.
11. History or current diagnosis of gastrointestinal bleeding or peptic ulcer disease.
12. Elevated transaminases (ALT and AST) at screening.
13. History of convulsions.
14. History of porphyria.
15. Relevant history or laboratory or clinical findings indicative of acute or chronic disease, likely to influence study outcome.

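### The diet rules leave capsaicin-containing food unrestricted although capsaicin is assayed in plasma, so diet could confound the Day 1 and Day 5 capsaicin samples

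*Protocol*

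**What the plan says.** Protocol section 7.2.10.2 (Diet) contains two food bans, both running until the last PK sample of the period. The first reads: "The ingestion of food and beverages containing citrus fruits and/or apple or pineapple will not be allowed for 72 hours before the administration of IMP". The second reads: "The ingestion of food and beverages containing alcohol and/or methylxanthines e.g., caffeine (coffee, tea and cola) will not be allowed for 24 hours". On clinic days, "Meals taken during the clinic stay will be standardized in regard to composition and time of administration", with the details left to the Source Document Agreement. At home, eating is free "unless restrictions apply, after the subjects have been discharged from the clinic". Neither ban names a capsaicin-containing food, and no other section of the protocol or SAP does so as a diet rule.

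The protocol does recognise food-plant sources of capsaicin, but only as an allergy exclusion (section 7.3.2, criterion 9): "History of hypersensitivity or allergy to cayenne pepper or other capsaicinoids (paprika plants".

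Capsaicin is listed as an analyte beside diclofenac. On expected exposure, section 5.2 reports that with higher strengths, in few patients, "low, transient levels of capsaicin can be detected in the systemic circulation". Table 7-2 (section 7.2.9) budgets capsaicin sampling for one treatment period only, in the rows "Capsaicin (Day 1) 4 10 1 40" and "Capsaicin (Days 5, 6 and 7".

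**The concern.** A diet rule in a PK study should cover foods that contain the analyte being measured. Here the list covers several foods but omits the one dietary source of an assayed substance that the protocol names elsewhere.

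The omission matters more than usual because little capsaicin is expected from the gel. If the product behaves as section 5.2 suggests, the capsaicin result will be mainly a listing of sporadic quantifiable samples. A sample that is positive because of a meal would then look the same as one that is positive because of absorption through the skin. There is little to tell them apart: no capsaicin profile is taken in the two diclofenac-only periods, and no food record is described (the diary card in section 7.2.6 is described for recording IMP administrations).

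At stake is the reading of the capsaicin data, meaning how often and when systemic capsaicin appears after the combination gel. The relative bioavailability of diclofenac is not at stake.

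**Working it through.** **1. Reproduce the plan's blood volume, to fix where capsaicin is sampled.** Inputs are the rows of Protocol Table 7-2. Formula: volume × samples × periods, summed, with 15 + 2(2) = 19 samples on Days 5 to 7.

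- Diclofenac, Day 1: 2 × 10 × 3 = 60 mL
- Capsaicin, Day 1: 4 × 10 × 1 = 40 mL
- Diclofenac, Days 5 to 7: 2 × 19 × 3 = 114 mL
- Capsaicin, Days 5 to 7: 4 × 19 × 1 = 76 mL
- Hematology: 4 × 2 = 8 mL
- Clinical chemistry: 5 × 2 = 10 mL
- Total: 60 + 40 + 114 + 76 + 8 + 10 = 308 mL, the stated figure

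The total holds only with capsaicin drawn in one period. Three periods would give 308 + 2 × (40 + 76) = 540 mL. The table does not name the period; I take it to be the combination period, since only Test Product 2 contains capsaicin. Capsaicin accounts for 40 + 76 = 116 of 308 mL, or 38%.

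**2. Count the samples.** 10 (Day 1) + 2 (Day 5) + 2 (Day 6) + 15 (Day 7) = 29 per subject. With the maximum of 48 subjects, 29 × 48 = 1,392.

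**3. Set each sample against the diet in force before it.** Clinic stays are from Protocol section 7.1.1 and sampling times from Table 7-1, notes 20 and 21.

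| Samples | Number per subject | Diet beforehand | Protection from dietary capsaicin |
|---|---|---|---|
| Day 1, 0 to 12 h | 10 | Home diet until Day -1 admission, then clinic meals | None before admission; clinic menu not stated |
| Day 5, before both doses | 2 | Home diet since Day 2 discharge | None |
| Day 6, before both doses | 2 | Clinic meals from the evening of Day 5 | Only if the menu is free of capsaicin |
| Day 7, 0 to 24 h | 15 | Clinic meals from the evening of Day 5 | Only if the menu is free of capsaicin |

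So 10 + 2 = 12 of 29 samples follow a recent stretch of unrestricted eating, and 2 + 15 = 17 rely on the clinic menu. With 48 subjects the Day 5 samples number 2 × 48 = 96 and the Day 1 samples 10 × 48 = 480. How far into the Day 1 profile a meal before admission could reach depends on how long dietary capsaicin persists in plasma, which the documents do not give.

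**4. Look for samples that could reveal a dietary background.** The Day 1 set includes a 0-hour sample before the first dose of the period. In Periods 2 and 3 it comes at least 7 calendar days after the previous product. It is off treatment, so the count is 1 of 29, plus 0 in the other two periods. It can show food eaten before that time point, but not food eaten on Days 2 to 5 or during either profile.

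**5. See where capsaicin enters the results.** The protocol synopsis treats capsaicin concentrations descriptively, and section 11.4.1 confines primary and secondary endpoints to diclofenac. SAP Addendum section 2.4 also derives the Day 7 exposure parameters for capsaicin, over the 0 to 12 hour interval set in section 2.2. Those come from samples that begin about 36 hours after re-admission (evening of Day 5 to morning of Day 7: 24 + 12). Protocol section 11.6 and SAP section 6.3.11 give summary statistics by time point only if at least 2/3 of individuals have numerical values.

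**The case against.** The case for leaving the plan alone has several sound parts.

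- **There is an off-treatment sample.** A reader might infer that nothing in the data could expose a dietary background. The Day 1 pre-dose sample contradicts that: it is drawn the morning after admission and so follows recent home eating. This stands, within the limit that one time point says nothing about later intake. SAP section 6.1.3.2 also has a rule for pre-dose values above 5% of the maximum, but redaction hides whether it covers capsaicin, so I rest nothing on it.
- **The derived parameters are largely shielded.** A reader might infer that the Day 7 capsaicin AUC and maximum are contaminated by free-living meals. By then subjects have been in-house for about 36 hours on standardised meals. The Day 5 samples serve to check steady state and do not enter the Day 7 parameters. This stands, provided the menu is free of capsaicin. The menu sits in an agreement that is not among the documents, so its content can be neither assumed nor faulted.
- **The size is unknown.** No section says how much dietary capsaicin reaches plasma or for how long, and no quantification limit is given. A reader might want a count of falsely positive subjects. Any such count would rest on a rate with no source here, so none is offered.
- **The 2/3 rule limits the damage.** If capsaicin is rarely quantifiable, stray positives appear in the listings and in the number of observations, not in a mean. This stands, but it also means the listing is what will be read.

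None of this supplies the missing diet rule, and standardised meals are not the same as capsaicin-free meals.

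**Conclusion.** The concern holds as a minor point. A subject who follows every diet rule can eat capsaicin-containing food shortly before Day -1 admission or between Day 2 discharge and re-admission on Day 5. That could confound the Day 1 and Day 5 capsaicin samples, with one pre-dose sample as the only off-treatment check and no capsaicin samples under the diclofenac-only gels for comparison. The Day 6 and Day 7 samples are safe only on the unstated condition that the clinic menu is free of capsaicin.

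This rests on two assumptions: that the single capsaicin period in Table 7-2 is the combination period, and that dietary capsaicin can reach measurable plasma levels. The documents neither confirm nor exclude the second.

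The reach is limited to the capsaicin results, which the protocol treats as descriptive. The documents do not support extending the point to the diclofenac comparison: its endpoints use no capsaicin level.

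**What to change.** In Protocol section 7.2.10.2, add food and beverages containing chili, cayenne, paprika or other capsaicinoids to the existing 72-hour restriction, running until the last PK sample of each treatment period. Repeat the line in the subject leaflet, because the exposed days are spent at home. Confirm in the Source Document Agreement that the standardised clinic menu contains none of these ingredients.

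The cost is one protocol sentence, one leaflet line and a menu check. The downside is one more food restriction for subjects. No sample, visit or staff time is added.

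Extra sampling would be a weaker remedy. One 4 mL pre-dose capsaicin sample in each of the other two periods would raise the total to 308 + 2 × 4 = 316 mL and still miss later intake. Full capsaicin profiles in all periods would need the 540 mL worked out above. Preventing intake costs less than trying to detect it.
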